8.5.2 Secondary Effectiveness Endpoint Analysis

Time to Discharge Eligibility- defined as elapsed time between removal of the final Mid-Bore VVCS device (treatment arm) or removal of the final sheath (control arm) and when the subject is eligible for discharge from the institution based on the assessment of the attending physician. The average time to discharge eligibility will be compared between the treatment and control groups at the 0.025 level of significance. The specific hypotheses being tested are:

Ho: $\mu_{Mynx \ Control} \geq \mu_{manual \ compression}$

Ha: $\mu_{Mynx \ Control} < \mu_{manual \ compression}$

where μ_x is the average time to discharge eligibility for the specified group. A p-value for this one-sided test less than 0.025 will indicate that the time to discharge eligibility for the subjects using the MYNX CONTROLTM Venous VCD was significantly less than for those where manual compression was used. The standard two group T-test will be used to make this comparison.

The difference between average times will also be calculated along with a 95% confidence interval based on the T-distribution.

The remaining secondary endpoint comparisons between MYNX CONTROL™Venous VCD and manual compression are considered ad hoc analyses.

If the distribution assumption of normality the secondary effectiveness endpoint does not hold based on Shapiro-Wilk test at the 0.05 alpha level, a non-parametric Wilcoxon rank sum test will be used to compare the treatment groups.

Procedural Success: attainment of final hemostasis at all venous access sites without major venous access site closure-related complications through 30 days. The proportion of subjects achieving procedural success will be calculated for each treatment group. Those proportions will be compared using both the Pearson Chi-square statistic and Fisher's Exact Test.

Device Success: ability to deploy the VCD delivery system, deliver the polyethylene glycol hydrogel sealant, and achieve hemostasis. This endpoint will be summarized for

the MYNX CONTROL[™] Venous VCD arm only. The proportion of devices that achieve success will be estimated along with a 95% confidence interval calculated using the Clopper-Pearson (exact binomial) method.

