	• Time to Discharge Eligibility - defined as elapsed time (in hours) between removal of the final MYNX CONTROL™ Venous VCD (device group) or removal of the final sheath (control group) and when subject is eligible for discharge from the institution based on the assessment of the attending physician.	
	 Procedural Success: attainment of final hemostasis at all venous access sites without major venous access site closure-related complications through 30 days 	
	 Device Success (for device group): ability to successfully deploy the MYNX CONTROL[™] Venous VCD delivery system, deliver the polyethylene glycol hydrogel sealant, and achieve hemostasis (device group only) 	
Additional Endpoints	Pain score at time of discharge eligibility.	
Sample Size	Total enrollment of 204 patients (2:1 randomized – 136 VCD: 68 manual compressions)	
Duration of Subject Participation	ALL patients will be followed through 30 days post procedure. Once all enrolled patients have completed follow-up, the study will be considered complete.	
Statistics/Testing Methods	Data analysis will follow the intention-to-treat principle and will be conducted at the per access site or per patient level as indicated below, with a non-inferiority analysis for primary safety endpoint and superiority analyses for primary and powered secondary effectiveness endpoint.	

Version: 3.0 / 31Jan2023

Table 1. Time and Event Schedule (Please refer to Section 14 for details)

	Screening (-30 to day 0)	At time of Index Procedure (day 0)	Post- Procedure/	Pre- discharge	1-Month (30 ± 7 days)
Informed consent (within 60 days of index procedure)	х				
Pre-op Inclusion / Exclusion Criteria Assessment	х				
Demographics	х				
Physical exam/Medical History	Х				Х
Laboratory Tests (PLT, WBC, HGB, HCT, creatinine, PT or INR)	X1				х
Intra-procedural Exclusion Criteria Assessment		X*			
Randomization		Х			
Study Endpoint Data Collection:					
TTH determination		Х			
TTA determination			Х		
TTDE determination			Х		
Device Success		Х			
Procedure Success					Х
Concomitant Medications (e.g., anti- platelet, anti-coagulant, anti-thrombotic agents, etc.)	х	х	Х		х
Post Op Pain assessment			Х		
Adverse Events		Х	x		X
Ultrasound Exam (DUS sub- study only)				X **	X ***

¹ Laboratory tests should be done within -7 to 0 days of index procedure

* Intra-op inclusion/exclusion criteria will be evaluated once operator is able to visualize and assess sheath

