16.9.1 Primary Analysis

Efficacy

The primary efficacy endpoints will be analyzed separately.

The average time to ambulation in each treatment group will be compared using a standard T-test.

The average time to hemostasis will be compared to the treatment groups using a generalized linear mixed model where subject is considered a random effect with multiple access sites. The times to hemostasis in the manual compression group will be reduced by 5 minutes to account for the hypothesis that the time to hemostasis for the MYNX CONTROL[™] Venous VCD is at least 5 minutes less than manual compression. The analysis will consist of testing the coefficient on the fixed effect for treatment group. If that coefficient is found to be significantly different from zero, then the direction will be evaluated to assure that the hemostasis time is reduced on average when using MYNX CONTROL [™] Venous VCD.

Safety

The safety analysis will be completed on a per-limb basis.

This endpoint will be analyzed using a GEE approach for a logistic regression model with a compound symmetric working covariance structure where occurrence of an AE is the binary response variable and treatment group is the only explanatory variable. Least square means for each treatment group and the risk difference between groups will be calculated along with the two-sided 95% confidence interval. The one-sided 97.5% confidence bound (equivalent to the appropriate bound from the two-sided 95% interval) will be compared to the non-inferiority window. If the upper bound is less than the non-inferiority window, then the two treatment groups will be considered non-inferior relative to the proportion of limbs experiencing a major venous access site closure-related complication.

As a supplementary analysis, a generalized linear mixed model will be used where subject will be entered into the model as a random effect and a compound symmetric correlation structure applied to those subjects contributing two limbs.

Version: 3.0 / 31Jan2023

Trial Success

This trial will be considered a success if both primary efficacy endpoints and the primary safety endpoint are achieved.

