16.9.3 Secondary Efficacy Analyses

Time to Discharge Eligibility, defined as the elapsed time between removal of the final MYNX CONTROL[™] Venous VCD (device group) or removal of the final sheath (control group), and when the subject is eligible for discharge from the institution (in hours) will be summarized on a perpatient basis.

Time to discharge eligibility is a powered secondary endpoint. The average time to discharge eligibility will be compared between the device and control groups at the 0.025 level of significance. The specific hypotheses being tested are:

Ho: $\mu_{Mynx \ Control} \geq \mu_{manual \ compression}$

Ha: $\mu_{Mynx \ Control} < \mu_{manual \ compression}$

where μ_x is the average time to discharge eligibility for the specified group. A p-value for this one-sided test less than 0.025 will indicate that the time to discharge eligibility for the subjects using the MYNX CONTROLTM Venous Vascular Closure Device (VCD) was significantly less than for those where manual compression was used. The standard two group T-test will be used to make this comparison.

The difference between treatment groups in average time to discharge will also be estimated with 95% confidence intervals calculated using the T-distribution.

The following secondary endpoints are considered ad hoc analyses and are not powered.

Procedural Success defined as the attainment of final hemostasis at all venous access sites without major venous access site closure-related complications through 30 days will be summarized on a per access site basis and on a per-limb basis. Procedural success will be estimated for each treatment group separately with 95% confidence intervals followed by an

Version: 3.0 / 31Jan2023

estimate of the difference in procedural success between the treatment groups and a 95% confidence interval on the difference.

Device Success defined as the ability to deploy the VCD delivery system, deliver the polyethylene glycol hydrogel sealant, and achieve hemostasis will be summarized on a per access site basis for the device group only. The proportion of device successes will be estimated along with a 95% confidence interval.

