Initial estimates for time to discharge eligibility were obtained from the VASCADE MVP Venous Vascular Closure System (Cardiva Medical Inc.) Summary of Safety and Effectiveness Data. The average time to discharge eligibility for VASCADE MVP Venous Vascular Closure System (Cardiva Medical Inc.) was 3.1±1.3 hours and for manual compression it was 6.5±1.9 hours. For sample size calculation, the Type 1 error rate was set to 0.025. A sample size of 23 subjects provides more than 95% power to demonstrate that the average time to discharge eligibility is significantly less for the MYNX CONTROL[™] Venous group relative to manual compression.

Study Sample Size:

The sample size for adequate power on the primary safety endpoint was the largest and will be used as the overall sample size for this trial.

The study also incorporates a DUS sub study with enrollment target of 72 randomized subjects. This substudy is not powered and does not impact the primary statistical design and the main analytical cohort of the first 204 subjects that are randomized .

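### Time to discharge eligibility has its own formal one-sided 0.025 test, but neither document states a testing order or ties that test to success on the primary endpoints

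*SAP*

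**What the plan says.** Both documents treat TTDE as a confirmatory comparison.

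- Protocol 16.9.3 gives its status: "Time to discharge eligibility is a powered secondary endpoint". The statistics entry in the Protocol Synopsis plans "superiority analyses for primary and powered secondary effectiveness endpoint".
- SAP 5 and Protocol 16.8 give it a separate sample size calculation. The assumed time for the reference closure device "was 3.1±1.3 hours and for manual compression it was 6.5±1.9 hours". On alpha, SAP 5 says: "For sample size calculation, the Type 1 error rate was set to 0.025".
- SAP 8.5.2 sets out null and alternative hypotheses and then the test level: "The average time to discharge eligibility will be compared between the treatment and control groups at the 0.025 level of significance". The decision rule begins "A p-value for this one-sided test less than 0.025 will indicate that the time to discharge eligibility for the subjects" and goes on to conclude that the device group's time was significantly shorter. Protocol 16.9.3 has the same rule.
- The remaining secondary comparisons between the device "and manual compression are considered ad hoc analyses" (SAP 8.5.2; Protocol 16.9.3 is to the same effect).

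The overall success rule is in Protocol 16.9.1: "This trial will be considered a success if both primary efficacy endpoints and the primary safety endpoint are achieved". It does not mention TTDE. The SAP states no overall success rule. Neither document says in what order the primary and TTDE tests are read, or what happens to the TTDE test if a primary endpoint is missed.

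**The concern.** The primary decision needs no alpha adjustment, because all three primary endpoints must succeed, each at one-sided 0.025. TTDE adds a second confirmatory statement with its own full 0.025. If that statement does not depend on the primary result, there are two separate chances of a false confirmatory claim, and their joint error is not held at 0.025.

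The practical side is interpretation. A programmer following SAP 8.5.2 would run the TTDE test and report significance whatever the primary results. If a primary endpoint had been missed, a dispute would follow over whether the TTDE p-value is confirmatory, and it would have to be settled after the data were known.

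**Working it through.** **1. The plan's own TTDE figure.** Inputs (SAP 5): means 3.1 and 6.5 h, SDs 1.3 and 1.9 h, 2:1 allocation, 23 subjects (taken as 15:8), alpha 0.025, stated power above 95%.

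- Difference = 6.5 − 3.1 = 3.4 h.
- Standard error = √(1.3²/15 + 1.9²/8) = √(0.1127 + 0.4513) = 0.751 h.
- Normal approximation: Φ(3.4/0.751 − 1.96) = Φ(2.57) = 99.5%.
- Pooled noncentral t: 99.8%. Welch noncentral t: 98.3%.

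The stated power is confirmed. At 136:68 the standard error is √(1.3²/136 + 1.9²/68) = 0.256 h and the ratio is 3.4/0.256 = 13.3, so power is above 99.9% on the same assumptions.

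**2. Error across the two claims as written.**

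- A false declaration of trial success has probability at most 0.025, because every primary must pass at that level.
- A false TTDE claim has probability at most 0.025.
- With no link between them, the bound is 0.025 + 0.025 = 0.050.

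The least favourable case is one primary null, the other primaries certain to pass, and TTDE null. The error is then 0.050 − P(both statistics exceed 1.96), with the two statistics taken as bivariate normal. The documents give no correlation, so the values below are assumptions.

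| Assumed correlation | P(both exceed 1.96) | Error across the two claims |
|---|---|---|
| 0 | 0.0006 | 0.0494 |
| 0.5 | 0.0046 | 0.0454 |
| 0.7 | 0.0083 | 0.0417 |
| 0.9 | 0.0148 | 0.0352 |
| 0.95 | 0.0177 | 0.0323 |

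At correlation 0 this is 1 − 0.975² = 0.0494.

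**3. Where in that range the trial probably sits.** TTA and TTDE both start at removal of the final device or sheath (Protocol 14.2). Note 2 of that section makes it a protocol deviation if discharge eligibility is delayed more than 30 minutes after successful ambulation for reasons unrelated to the access site. TTDE should therefore be largely TTA plus a short interval. Two things follow. The TTA and TTDE statistics should be strongly correlated. And if TTDE is null, TTA is likely to be close to null, so it is not certain to pass as the least favourable case requires. Both pull the error toward the lower end, even if the failing primary is safety, because a false trial success would still need TTA to pass.

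**4. Error with a gate.** If any primary is null, a TTDE claim can arise only inside a false trial success, which has probability at most 0.025. If all primaries are truly met, only the TTDE claim can be false, again at most 0.025. The error across both claims is at most 0.025 in every case.

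**5. How often the missing order would come into play.** This is not an error rate. Stated powers: TTA 90%, safety about 80%, TTH about 95% at 150 patients.

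- Scaling TTH to the enrolled size: (1.960 + 1.645) × √(204/150) = 4.204, and Φ(4.204 − 1.960) = 0.988. At 194 patients (5% attrition) the result is 0.984. Take 0.985.
- If the three are independent (an assumption): 0.90 × 0.985 × 0.80 = 0.709, so at least one primary is missed in about 29% of trials.
- Whatever the dependence, that chance lies between 20% (safety alone) and 0.10 + 0.015 + 0.20 = 31.5%.

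**The case against.** The strongest case against is that this is silence on a modest secondary matter. Four parts of it stand.

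- A reader might infer that the plan directs TTDE to be tested even after a primary failure. No sentence says so. The documents give an alpha and a decision rule and are silent on order.
- A reader might infer that TTDE could rescue a failed trial. It cannot: Protocol 16.9.1 leaves it out of the success rule. The proposed indication (Protocol 4) names times to hemostasis and ambulation, not discharge, and neither document announces a labelling claim on TTDE.
- A reader might take the 29% as a rate of false claims. It is not. It is computed under the design assumptions, where TTDE truly differs by 3.4 h, so a TTDE rejection in those trials would be correct.
- The 4.9% figure needs independent statistics and a null TTDE alongside primaries that are sure to pass. The link between TTA and TTDE makes that configuration unlikely.

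What does not stand is the step from these limits to no action. TTDE has hypotheses, a power calculation and a significance rule, and it is set apart from the comparisons labelled ad hoc. A test specified in that way needs a stated place in the testing order.

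**Conclusion.** The point holds as a gap in the testing strategy. The plan pre-specifies a significance statement for TTDE without saying that it depends on the primary endpoints. The one-sided error across the trial-success and TTDE claims is bounded by 5.0%, against 2.5% with a gate. In the least favourable case it is about 3.2% to 4.9% for assumed correlations from 0.95 to 0, probably toward the lower end. On the design assumptions, with independence also assumed, the missing order would matter in about 29% of trials.

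The sample size, the primary tests and the trial-success decision are all unaffected. The co-primary efficacy endpoints and primary safety need no alpha adjustment among themselves. The change is worth making because it is nearly free and settles the status of the TTDE p-value in advance.

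**What to change.** Add one sentence to both SAP 8.5.2 and Protocol 16.9.3, for example: *TTDE will be formally tested at one-sided 0.025 only if TTA, TTH and the primary safety endpoint are all met; otherwise its p-value and confidence interval will be reported as nominal and descriptive.*

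The success rule in Protocol 16.9.1 should also be repeated in the SAP, so that the condition has something to refer to there.

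Cost: no primary alpha is used, N stays at 204, and TTDE power once the gate is passed remains above 99.9% on the plan's assumptions. What is given up is a confirmatory TTDE statement from a trial that misses a primary endpoint. The sentence should be added before comparative data are reviewed.

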8.6 Adverse Events

Adverse events (AE), Serious Adverse Events (SAE), Major Adverse Events (MAE), and Unanticipated Adverse Device Effects (UADE) will be tabulated (or listed) separately for each treatment group. The table or listing will contain the term or description, start and end dates, severity, outcome, and causality or association to the investigational product or procedures involved in the clinical study. These summary tables will present descriptive statistics and no formal testing will be done.

8.7 Sub-Group Analysis

A sub-group analysis will be completed for the primary safety and primary efficacy endpoints as outlined in Section 8.5. This analysis is not powered and is strictly for information purposes. The sub-groups are:

- Race
- Sex (females vs. males)
- Total Number of access sites
- Number of access sites per limb
- Sheath size
- Number of limbs (1 vs. 2)

Of the identified sub-groups, the following groups: the total number of access sites, Number of access sites per limb, sheath size and the number of limbs subgroup will be analyzed for both the major and minor complications noted within the study between both treatment groups.

For time to ambulation and time to hemostasis, homogeneity of the treatment will be tested using a linear model. Treatment group will be one factor while sub-group will be the second factor in the model and an interaction term between treatment group and sub-group will be added to the model. The interaction term will be tested at the 0.15 level of significance. If the p-value is greater than 0.15 then the treatment effect will be considered homogeneous. For the safety endpoint, homogeneity of the major venous access site closure-related complication rate through 30 days post-procedure will be modeled using a logistic regression model. As for the effectiveness endpoint, a treatment group by sub-group interaction will be added to this model and tested at the 0.15 level of significance. If the p-value is greater than 0.15 then the major complication rates will be considered homogeneous.

A sub-group analysis will also be performed utilizing independent analysis of noninvasive duplex ultrasound (DUS) imaging in 48 subjects from the MYNX CONTROL[™] group and 24 subjects from the manual compression group at the time of the procedure, pre-discharge and potentially again at the 30-day follow-up. Specific investigational sites will be designated as ultrasound sites. These sites will include subjects in the ultrasound subset imaging until a total of 72 patients have been evaluated (48 MYNX CONTROL[™], 24 Manual Compression). Ultrasound will be performed at the follow-up office visit only if a complication was detected at discharge. All sub-study sites will be instructed in performance of duplex ultrasonography of the femoral vascular structures.

Images will be interpreted by the following central core laboratory:

NAMSA [name]

At the time of the procedure, and at discharge, the proportion of subjects exhibiting a complication on DUS imaging will be calculated along with 95% confidence intervals constructed using the Clopper-Pearson method. For those subjects that required a DUS at the 30-day follow-up, the proportion of subjects still exhibiting a complication will be calculated along with a 95% confidence interval constructed using the Clopper-Pearson method.

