2.2 Structural composition, operation principle and mechanism of action

The MYNX VCD product family are designed to achieve hemostasis of femoral access sites following diagnostic or interventional endovascular procedures. Hemostasis is accomplished via delivery of an extravascular polyethylene glycol (PEG) sealant using a balloon catheter (delivery system) in conjunction with a standard procedural sheath. Upon contact with blood and subcutaneous fluids, the sealant expands and adheres to the arteriotomy or venotomy to achieve hemostasis. The sealant is resorbed by the body within 30 days.

The design of the MYNX CONTROL[™] Venous VCD is based on the design of the current MYNX CONTROL[™] VCD (arterial). The only difference in design is the Sheath Catch. The Sheath Catch facilitates the withdrawal of the 6F/7F Catheter Sheath Introducer (CSI) from the tissue tract during the withdrawal of the MYNX CONTROL[™] VCD (current). This is achieved by a distal hook which latches onto the sideport on the CSI. The proposed sheath catch design on the MYNX CONTROL[™] Venous VCD will be based on the current design but will allow larger CSIs (up to 12F) to fit into the Sheath Catch. Like the current Sheath Catch design, connection to the CSI will be achieved with a distal hook and be universally compatible with the leading CSI brands on the market.

Figure 1: MYNX CONTROL™ Venous Vascular Closure Device 6F-12F

3 Study Objectives

To demonstrate safety and efficacy of the MYNX CONTROL[™] Venous Vascular Closure Device 6F-12F vs. manual compression in sealing femoral venous access sites in patients who have undergone endovascular procedures utilizing one or more procedural sheaths up to 12F.

Version: 3.0 / 31Jan2023

4 Indication

Proposed Indications for Use:

The MYNX CONTROL[™] Venous VCD 6F-12F is indicated for use to seal femoral venous access sites while reducing times to hemostasis and ambulation in patients who have undergone diagnostic or interventional endovascular procedures utilizing 6F to 12F procedural sheaths, with single or multiple access sites in one or both limbs.

5 Contraindications

There are no known contraindications for the MYNX CONTROL[™] Venous Vascular Closure Device 6F-12F.

6 Precautions

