16.10 Sub-Group Analysis

A sub-group analysis will be completed for the primary safety and primary efficacy endpoints. This analysis is not powered and is strictly for information purposes. The sub-groups for this analysis are those subjects that contributed only 1 limb and those subjects that contributed 2 limbs. The same analysis outlined above for the primary safety and efficacy endpoints will be completed within each sub-group separately. Additional analyses to demonstrate the homogeneity of the treatment effect and homogeneity of the major complication rates are detailed in the SAP.

Major and minor complications will also be analyzed based on the number of access sites and sheath size, major and minor complications will be stratified by number of access sites per leg (1, 2, 3, or 4 sites), total number of access sites per patient (1, 2, 3, or 4 sites), and sheath size (small size vs. large size). Details are provided in the SAP.

A sub-group analysis will also be performed utilizing independent analysis of non-invasive duplex ultrasound (DUS) imaging in 72 subjects from both arms (48 device and 24 control) at the time of the procedure, pre-discharge and potentially again at the 30-day follow-up (only for those subjects that have documented evidence of access site complications at the discharge ultrasound). Specific investigational sites will be designated as ultrasound sites. These sites will include subjects in the ultrasound subset imaging until a total of 72 patients have been evaluated in both treatment arms. Ultrasound will be performed at the follow-up office visit only if a complication was detected at discharge. All sub-study sites will be instructed in performance of duplex ultrasonography of the femoral vascular structures. Images will be interpreted by:

NAMSA [name]

Version: 3.0 / 31Jan2023

[name]

At the time of the procedure, and at discharge, the proportion of subjects exhibiting a complication on DUS imaging will be calculated along with 95% confidence intervals constructed using the Clopper-Pearson method. For those subjects that required a DUS at the 30 day follow-up, the proportion of subjects still exhibiting a complication will be calculated along with a 95% confidence interval constructed using the Clopper-Pearson method.

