5 SAMPLE SIZE

All sample sizes were calculated assuming a 2:1 ratio of MYNX CONTROL[™] VCD to manual compression.

Time to Ambulation:

Time to ambulation is a co-primary endpoint for effectiveness. The Type 1 error for this calculation was set at 0.025 for a one-sided test. Assuming that the treatment group ambulates in 3.0 hours on average and the control group ambulates in 6.0 hours and both groups have a standard deviation of 6.0 hours, then an effective sample size of 192 subjects provides 90% power to detect this difference in time to ambulation between the two groups of subjects. Adjusting for a missing data rate of 5%, total enrollment is 204 subjects.

Time to Hemostasis:

Time to hemostasis is a co-primary endpoint for effectiveness. The Type 1 error for this calculation was set at 0.025 for a one-sided test. A generalized linear mixed model will be used to compare the MYNX CONTROL[™] Venous VCD device with manual

compression (control). Initial estimates of the average time to hemostasis were taken from historical MYNX family devices and compared to manual compression. Previous MYNX family studies only studied one access site per subject within the femoral artery. The observed average time to hemostasis as well as the standard deviations of those measurements helped inform the design of this trial where the standard deviation would be used as an estimate of subject-to-subject variation. For the sample size calculation, it is assumed that each subject has 3 access sites in the femoral vein. These access sites will be closed with either the MYNX CONTROL[™] Venous VCD device or manual compression. Only one method of closure will be used per subject. Time to hemostasis will be measured for each access site separately.

It is assumed that hemostasis times are log-normally distributed. Using previous study data where time to hemostasis averaged 6 minutes for the MYNX CONTROLTM Venous VCD device and 13 minutes for manual compression, estimates of μ and σ of the lognormal distribution were obtained and used in the calculation of sample size for this endpoint.

A generalized linear mixed model is used with the subject as a random effect. The specific model used is:

$$y_{ijk} = \mu + \tau_i + S_{j(i)} + e_{k(ij)}$$

where τ_i is the treatment effect and S_{ij} is the random effect of subject within treatment. e_{ijk} is the unexplained variation in the model. Further, it is assumed that:

$$y_{ijk} \sim N(\mu_{ij}, \sigma^2)$$

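### SAP 8.7 concludes from an interaction p-value above 0.15 that the time-to-ambulation effect is homogeneous, which an unpowered test with no margin and no interaction confidence interval cannot support

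*SAP*

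**What the plan says.** SAP 8.7 lists six sub-group factors: race, sex, total number of access sites, access sites per limb, sheath size and number of limbs. For the effectiveness endpoints it states: "For time to ambulation and time to hemostasis, homogeneity of the treatment will be tested using a linear model". The model holds treatment, sub-group and their interaction. "The interaction term will be tested at the 0.15 level of significance" The decision rule follows: "If the p-value is greater than 0.15 then the treatment effect will be considered homogeneous".

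The same section says of the sub-group work: "This analysis is not powered and is strictly for information purposes". Protocol 16.10 nevertheless describes what the SAP will add as "Additional analyses to demonstrate the homogeneity of the treatment effect".

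Neither document gives the expected sub-group shares, the power of the interaction test, the amount of heterogeneity to be ruled out, or a confidence interval for the interaction.

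**The concern.** A test that fails to reject does not establish its null hypothesis. To conclude that an effect is uniform, one needs a stated margin and an interval narrow enough to lie inside it. SAP 8.7 has neither, says it has no power, and still prespecifies a positive verdict. The defect is visible in the wording, and needs no scenario.

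It deserves correction because of the factors involved. The proposed indication (Protocol section 4) covers "6F to 12F procedural sheaths, with single or multiple access sites in one or both limbs". Sheath size, number of access sites and number of limbs are the dimensions on which the rule would pronounce the TTA effect uniform, and a prespecified statement of homogeneity could be read as support for that breadth.

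TTA is the clearest case. It is a per-subject continuous endpoint, so the linear model itself is suitable, and the problem lies only in the conclusion drawn from it. The rule also covers time to hemostasis, but the figures below are for TTA.

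**Working it through.** **Inputs from SAP section 5.** "Assuming that the treatment group ambulates in 3.0 hours on average and the control group ambulates in 6.0 hours", so the planned effect is 3 h. Also "both groups have a standard deviation of 6.0 hours". Allocation is 2:1, with 192 evaluable (128 versus 64), one-sided 0.025, 90% power, 5% missing and 204 enrolled. The interaction level of 0.15 is from SAP 8.7.

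**The plan's own figure.** Control n = (1.960 + 1.282)² × 6² × (1 + 1/2) / 3² = 63.04, rounded up to 64, which gives 192 in total. Then 192/0.95 = 202.1, rounded up to 203, or 204 at 2:1. Power with 64 controls is 90.1% by the noncentral t. The planned sample size reproduces.

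**Precision of a two-level interaction.**
- SE of the overall difference = 6 × √(1/128 + 1/64) = 0.919 h.
- SE of the interaction = 0.919 × √(1/f + 1/(1−f)), where f is the share of one sub-group.
- 95% half-width = 1.973 × SE (188 df).

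**Chance that p > 0.15**, by noncentral t with 188 df (two-sided critical value 1.445), with no benefit in the sub-group of share f and 3 h in the other. The shares are assumptions.

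| Share f | SE (h) | 95% half-width (h) | Declared homogeneous |
|---|---|---|---|
| 50% | 1.84 | 3.6 | 42% |
| 30% | 2.00 | 4.0 | 48% |
| 20% | 2.30 | 4.5 | 55% |
| 10% | 3.06 | 6.0 | 67% |

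At the enrolled 204 instead of 192, the first and last rows become 40.5% and 66%. A simulation at 204 gave 40.2% and 65.5%.

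**How far the result moves with the scenario** (192 evaluable):
- Overall mean effect held at 3 h, so that the benefiting sub-group gains 3/(1−f) h: 3.5% (50%), 24% (30%), 42% (20%), 63% (10%).
- SD 3 h, no benefit versus 3 h: 3.5% (50%) to 30% (10%).
- SD 3 h, benefit halved in one sub-group (1.5 h versus 3 h): 42% to 67%, because the ratio of interaction to SD is the same as in the table.
- SD 6 h, benefit halved: 72% to 80%.
- Four levels with equal shares, one without benefit, SD 6 h (noncentral F, 3 and 184 df): 63%. The SAP gives no levels for the TTA test. The 1 to 4 sites in Protocol 16.10 are for complications.

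**Joint with the primary test.** With 3 h in one sub-group and none in the other, the overall effect shrinks to 3 × (1−f) h. In simulation (40,000 runs, SD 6 h), a significant primary TTA test together with interaction p > 0.15 occurred in 15% of trials at 50/50, about 30% at 30/70, 40% at 20/80 and 56% at 10/90.

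**The case against.** The strongest reply is that nothing depends on this rule. SAP 8.7 labels the analysis informational. Protocol 16.9.1 makes success depend only on the two primary efficacy endpoints and the primary safety endpoint. No section ties the indication to the interaction test. This stands, and it limits the weight of the point. It does not make the stated inference valid: an information-only analysis has no need of a prespecified verdict.

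A second reply is that sub-group results would be visible anyway. Protocol 16.10 repeats the primary analyses within the one-limb and two-limb groups, SAP 8.7 applies the section 8.5 analyses by sub-group, and SAP 8.1 provides means, SDs and 95% CIs as appropriate. This is largely right. What is absent is an interval for the interaction itself, the quantity the verdict concerns.

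A third reply is that SD 6 h may be too large. Protocol 14.2 requires device subjects to attempt ambulation within 2 to 2.5 h. The only related SDs in the documents are 1.3 and 1.9 h, for discharge eligibility with another device and its control. These are not TTA SDs, but a smaller SD would make a complete loss of benefit much harder to miss, as the SD 3 h figures show.

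A reader might also infer that the plan would usually report a uniform TTA benefit when one sub-group gains nothing. The documents do not support that. Such a report also needs a significant primary test, and the two coincide in 15% to 56% of trials in the illustrated scenario, exceeding half only for the smallest sub-group.

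**Conclusion.** The rule is wrong as a rule of inference, and Protocol 16.10 compounds it by speaking of demonstration. This conclusion rests on the text alone. The size of the problem at the planning values is best expressed by the interval: the interaction would be known only to within about ±3.6 h (even split) to ±6.0 h (10/90), against a planned effect of 3 h.

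The 42% to 67% chance of declaring homogeneity is an illustration. It might be read as following from the sample size and SD alone, but it also assumes two levels, the sub-group shares, and exactly 3 h benefit in the other sub-group, none of which the documents give. Other readings give 3.5% to 63% (overall mean held at 3 h) or 3.5% to 30% (SD 3 h).

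Nor do the documents support reading this as a flaw in the confirmatory analysis. It is a minor point about the conclusion an informational analysis is allowed to draw.

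**What to change.** In SAP 8.7, replace the homogeneity sentence for the effectiveness endpoints with:

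*The treatment difference in each sub-group and the interaction will be reported with 95% CIs; p > 0.15 will be reported as heterogeneity not detected and will not be taken as evidence of a homogeneous effect.*

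Keep the 0.15 test as a flag for heterogeneity. In Protocol 16.10, change *demonstrate* to *explore*.

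The cost is wording in two documents and an interval from the model already planned, with no new data or sample size. The downside is that the report can no longer state that the effect is homogeneous.
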